6.7 Laboratory Evaluations

6.7.1 Pharmacokinetic Specimens

Opportunistic blood collection for PK analysis will occur at the Week 4 and Week 8 visits. Samples will be derived from the plasma matrix.

Collect study product information for up to 8 doses prior to the sampling dose (last dose prior to PK biological sample collection):

- Exact date and time of previous study product dose administration
- Dose amount
- Dose number
- Dose frequency
- Dosing weight
- Actual weight from physical exam at corresponding week
- Height from physical exam at corresponding week
- Formulation (i.e., capsule swallowed or capsule contents mixed with food)
- Food intake [yes (fed); no (fasted)]
- If food intake yes, please enter what food was mixed with contents

Sampling Information to be collected at time of blood draw:

- Exact date and time the sample is drawn
- Exact date and time the sample is frozen/stored
- Sample volume (estimated)
- Sample type (i.e., plasma, whole blood, etc.)
- Source of blood sample (i.e., arterial vs. venous)
- Sampling site

Concomitant Medications of Interest Information:

- Presence of concomitant medications of interest* within 24 hours before and after the dose of study product closest to the time of biological sample collection
- Total dose amount (per day)
- Route of administration

*Only concomitant medications of interest (see Section [6.17](#)) for specific drugs will be recorded on the eCRF.

Timing of Sample Collection: Preferred Sampling Windows for PK include:

- 1) Peak sample: within 30 to 120 minutes *after* study product dose*
- 2) Trough sample: within 60 minutes *prior to* next study product dose*

*Samples obtained outside those windows are not protocol deviations.

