Prescribing guidelines report differences in pharmacokinetics and exposure between GIR and GER, and note that a dose substitution on a milligram for milligram basis will result in differences in exposure (INTUNIV® label).²⁶ GIR is 80% bioavailable and the relative bioavailability of GER tablets to GIR tablets is 58%. Compared to GIR, the Area Under the

Curve (AUC) and maximum serum concentration (Cmax) of GER tablets are 43% and 60% lower, respectively. Peak plasma concentrations occur 1 to 4 (average 2.6) hours after a single oral dose of GIR in adults and adolescents with hypertension and 5 hours after oral administration of extended-release tablets to children and adolescents with ADHD. However, studies have found that similar pharmacokinetics can be achieved between formulations. For example, plasma trough concentrations were similar in adults treated for smoking cessation with 3 mg/day administered BID of GIR and 4 mg/day of GER (3 mg/day GIR: M=3.40 ng/mL, standard error (SE) 0.34 vs. 4 mg/day GER: M=3.46 ng/mL, SE=0.67) with similar safety profiles between formulations.²⁹

The GER formulation is a practical challenge to prescribe in children with DS because the pill cannot be crushed and must be swallowed whole, and children with DS are at a high risk for comorbid dysphagia and swallowing dysfunction that puts them at significant risk for aspiration.³⁰ Safely swallowing tablets is a challenge. Children with DS have also been shown to have high risk for sleep apnea and baseline diminished blood pressure profiles compared to age-matched controls,³¹ thus this elevates the safety concerns for sedation and hypotension as known side effects that could be prolonged with an extended release formulation. As such, providers are using GIR to treat ADHD in children with DS in clinical practice with dosing strategies guided by the monitoring of side effects as doses are escalated. No formal dosing guidance exists for this population.

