6 STUDY PROCEDURES

6.1 Summary of Procedures

Table 1. Schedule of Study Procedures and Assessments

	Screening	Study Intervention (Weeks 1-3)	Study Intervention (Week 4)	Study Intervention (Weeks 5-7)	Study Intervention (Week 8)	Taper/Bridge	Follow-Up	Early Withdrawal/ Discontinuation
	Day -29 to 0 ¹	Day 1 ¹⁻²¹ (± 1 day)	Day 22-28 (± 3 days)	Day 29-49 (± 1 day)	Day 50-56 (± 3 days)		5 (+ 2) days post final study dose	
Informed consent/assent	X							
Distribution of device for remote HR and BP assessment		X ³						
Demographics	X							
Medical History	X							
Physical Exam	X	X ³						
Weight/height			X		X			
Vital Signs	X	X ³	X		X			
Concomitant Medications of Interest	X		X		X			
ECG	X		X		X			X
Lab assessments	X		X ¹¹					
Pregnancy test ¹³	X							
Blood Collection for PK			X ²		X ²			X ²
Randomization		X ³						
Dose escalation with HR and BP assessment		X ⁴	X ⁴	X ⁴				
Study product administration		X ⁵	X	X	X			
Unmasking					X			X
Study drug taper/bridge						X ⁶		X
Study Diary			Continuous			X ⁶	X ⁶	
CGI-S	X							
CGI-I		X ⁷	X	X ⁷	X			X
ABC	X		X		X			X
asQ Tool ¹²	X		X		X			
Sleep assessments		X ³	X		X			
Safety Events ⁸	X ⁹	X	X	X	X	X	X ¹⁰	X

1 – Day 0 and Day 1 may be the same calendar day.

2 – Preferred sampling: within 60 minutes prior to study product dose or 30-120 minutes after study product dose.

3 – Randomization; distribution of device for remote HR and BP assessment; physical exam, including weight/height; vital signs; and sleep assessments occur only on Day 1 prior to study product administration.

4 – Just prior to dose escalation time point, every 5 (+ 2) days, parent/legal guardian will be asked to measure HR and BP.

5 – Initial dose occurs on Day 1, Day 0 and Day 1 may be the same calendar day. The initial dose will be administered before bedtime on Day 1. Subsequent doses occur according to Section [6.13.1](#).

6 – For GIR arm only. Participants who choose to discontinue GIR will be tapered off study drug at 1 mg every 3 days. Participants who choose to transition to standard of care GIR will continue on up to 7 days of study drug to bridge to standard of care GIR. See Section [6.13.2](#).

7 – Weekly CGI-I, beginning at first weekly telephone assessment.

8 – Includes AEs, SAEs, and safety ESIs, as described in Section [7.1.2](#).

9 – Only AEs directly related to study procedures (e.g., blood collection) during the screening period will be collected.

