10.2.3 Exploratory Endpoints

The following PK endpoints will be estimated at Week 4 and Week 8:

- Guanfacine HCl plasma concentrations ($C_{\max,ss}$ and $C_{\min,ss}$)
- Time at peak concentration ($T_{\max,ss}$)
- Apparent area under the concentration versus time curve at steady state (AUC_{ss}/F)
- Apparent clearance (CL_{ss}/F)
- Volume of distribution (V/F)
- Half-life ($t_{1/2}$)

The following will be used to characterize the exposure-response relationship of GIR for the treatment of hyperactivity/impulsivity, inattention, and sleep quality in children with DS at Week 4 and Week 8:

- Guanfacine HCl plasma concentrations ($C_{\max,ss}$ and $C_{\min,ss}$)
- Area under the concentration time curve (AUC_{ss})
- ABC-H subscale score
- CGI-I

- Epworth Sleepiness Scale for Children and Adolescents (ESS-CHAD)
- Child's Sleep Habits Questionnaire (CSHQ)

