10.4.3 Exploratory Analysis

Exploratory Analysis 1: Characterize GIR exposure in children with DS.

The dosing, sampling, and demographic information collected by the study will be merged with bioanalytical information to create a PK dataset for GIR. Because a sparse sampling scheme will be employed in this study, population PK will be used to characterize GIR PK. If a relationship between exposure and response is observed, population PK or exposure-response models may be developed.

A detailed description of PK/PD analyses will be described in the PK Analysis Plan. Briefly, the following analyses are anticipated depending on the adequacy of the collected data:

Population PK Analysis

Pharmacokinetic (PK) models for the pooled concentration data of GIR will be explored by non-linear mixed effects modeling using NONMEM or Phoenix NLME software. Appropriate compartmental models will be examined, and between-participant variability on model parameters will be explored. Covariate analysis will examine the correlation between model parameters with demographic factors (e.g., weight, body mass index (BMI), sex, race, lab values, and obesity status) and co-administered medications. Appropriate covariates will be incorporated into the model using a standard forward-addition backward-elimination technique. Standard model diagnostic plots and procedures will be used to evaluate model appropriateness. Empiric Bayesian estimates of individual participant PK parameters will be generated from the final model. Model evaluation will be performed by visual predictive check and bootstrapping procedures, as needed.

As appropriate, the following apparent PK parameters may be estimated at steady state: systemic clearance (CL_{ss}/F), volume of distribution (V/F), maximum concentration ($C_{max,ss}$), minimum concentration ($C_{min,ss}$), half-life ($t_{1/2}$), and area under the curve (AUC_{ss}/F). Other PK parameters may be estimated according to the adequacy of sampling.

Exploratory Analysis 2: Characterize the exposure-response relationship of GIR for the treatment of hyperactivity/impulsivity, inattention, and sleep quality in children with DS.

Exposure-Response (ER) Analysis:

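### The preferred post-dose PK window closes before the protocol's own average GIR peak time and leaves the middle of the dosing interval unsampled, so V/F, half-life and Tmax,ss will be less precise than they need be

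*Combined protocol and SAP*

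**What the plan says.** Section 6.7.1 describes the collection as opportunistic: "Opportunistic blood collection for PK analysis will occur at the Week 4 and Week 8 visits". It then gives two preferred windows, a trough in the 60 minutes before the next dose and "Peak sample: within 30 to 120 minutes" after a dose. A note adds: "Samples obtained outside those windows are not protocol deviations". Table 1, footnote 2, repeats the windows but joins them with an or: "Preferred sampling: within 60 minutes prior to study product dose or 30-120 minutes after study product dose". Neither place says how many samples are drawn per visit.

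On the time of peak, Section 2.1.1 says: "Peak plasma concentrations occur 1 to 4 (average 2.6) hours after a single oral dose of GIR in adults and adolescents with hypertension". I found no other GIR peak time in the document, and no reason given for closing the window at 2 h.

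Sections 3 and 10.2.3 list Cmax,ss, Cmin,ss, Tmax,ss, AUCss/F, CLss/F, V/F and half-life as exploratory endpoints ("The following PK endpoints will be estimated at Week 4 and Week 8"). Section 10.4.3 sets the method: "Because a sparse sampling scheme will be employed in this study, population PK will be used to characterize GIR PK". It makes the parameter list conditional on the adequacy of the data, and that list does not name Tmax,ss.

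**The concern.** A sample labelled as the peak is requested over an interval that ends before the average peak time the protocol itself reports. The two preferred windows are also narrow clusters. With twice-daily dosing about 12 h apart, nothing is requested from 2 h to about 11 h after a dose. A population model does not need a sample exactly at the peak, but it does need samples spread over the interval to separate absorption, volume and elimination.

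What is at stake is how well V/F, half-life and Tmax,ss can be described. Section 4.9 says there are no PK data for GIR specific to children with DS, so no data in this population exist to fill the gap. Section 4.8 counts the plasma samples for drug exposure among the purposes of the design.

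**Working it through.** The peak time is a cited figure with no derivation in the document, so there is nothing to reproduce. The check has three steps.

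**1. Overlap of the two intervals.** Window 0.5–2 h (Section 6.7.1); peak range 1–4 h, average 2.6 h (Section 2.1.1).
- Window end to average peak: 2.6 − 2.0 = 0.6 h.
- Overlap: 2 − 1 = 1 h of the 3 h range. The first 0.5 h of the 1.5 h window precedes the earliest peak.
- Gap with no preferred time, for an assumed 12 h interval: from 2 h to 12 − 1 = 11 h.

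**2. Where the peak lies at steady state.** The visits are at steady state on twice-daily dosing (Section 6.13.1), not after a single dose. Use a one-compartment oral model with τ = 12 h:

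C(t) = [D·ka / (V(ka − ke))] × [e^(−ke·t)/(1 − e^(−ke·τ)) − e^(−ka·t)/(1 − e^(−ka·τ))]

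The document gives no half-life, so 10, 14 and 18 h are assumed, with ke = ln 2 / half-life. ka is solved so that the single-dose Tmax, ln(ka/ke)/(ka − ke), equals 2.6 h. Then Tmax,ss = ln{ka(1 − e^(−ke·τ)) / [ke(1 − e^(−ka·τ))]} / (ka − ke).

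| Half-life | ke (/h) | ka (/h) | Tmax,ss | Level at 0.5 h | at 1 h | at 2 h (share of Cmax,ss) |
|---|---|---|---|---|---|---|
| 10 h | 0.0693 | 1.149 | 2.07 h | 80% | 93% | 100% |
| 14 h | 0.0495 | 1.309 | 1.96 h | 85% | 95% | 100% |
| 18 h | 0.0385 | 1.428 | 1.88 h | 88% | 97% | 100% |

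The modelled steady-state peak sits at the edge of the window, and the curve is flat there.

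**3. Precision of the parameters.** First-order population information: F = N × mean of JᵀS⁻¹J. J holds the derivatives of log concentration with respect to log CL/F, log V/F and log ka, and S = JΩJᵀ + σ²I. Relative SEs come from F⁻¹, with half-life taken as ln 2 × V/CL. N = 60 × 2/3 × (1 − 0.20) = 32 children on GIR (Sections 4.2.1 and 10.6). Assumed, not in the document: between-child SD 30% on each parameter, residual 15%, one post-dose and one trough sample (11–12 h) per child, all inside the preferred windows. Relative SEs for half-lives of 10 / 14 / 18 h:

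| Parameter | Post-dose 0.5–2 h | Post-dose 0.5–4 h |
|---|---|---|
| V/F | 34 / 35 / 38% | 16 / 18 / 20% |
| Half-life | 28 / 31 / 34% | 15 / 17 / 20% |
| Tmax,ss | 37 / 45 / 54% | 26 / 34 / 42% |
| Cmax,ss | 8 / 8 / 7% | 5 / 5 / 5% |
| CL/F (and so AUCss, which is dose/CL) | 8 / 7 / 7% | 6 / 6 / 6% |

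Sensitivity:
- *Larger variability (40% and 25%):* V/F goes from 52–60% to 24–32%.
- *Trough and post-dose sample at both visits, with the post-dose draw at 0.5–2 h at one visit and 2–4 h at the other:* V/F goes from 21–24% to 10–14%, and Tmax,ss from 22–34% to about 13–23%.
- *Window moved to 1–4 h instead of widened* (other assumptions: half-life 8–24 h, 36 children, between-child CV 30% on CL and V and 60% on ka, residual 20%): V/F and half-life SEs under the current windows are 1.5 to 2.3 times larger. The absorption rate, which drives Tmax, improves at half-lives of 8 and 12 h but worsens at 17 and 24 h. The early samples are worth keeping.
- *One draw per visit, 0.5–2 h at one and 2–4 h at the other, with no trough:* V/F rises to about 55–95% and half-life to 68–108%, worse than the current plan.

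**The case against.** The strongest reply is that the plan is already flexible. The windows are preferences, out-of-window samples are not deviations, and exact dose and draw times are recorded with up to 8 earlier doses, so a population model can use a sample at any time. The calculation assumes that every sample falls inside the windows. If a quarter of the post-dose samples fell at 2–6 h (an assumption; the document gives no figure), the relative SE of V/F would already be about 19–26%. This stands as a limit on the size of the loss. It does not remove the point, because the stated preference is the only timing guidance the protocol gives sites, and it points away from the later times.

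A second reply is that the 2.6 h figure is a single-dose value in adults and adolescents with hypertension, while this trial samples children on capsules of milled tablets, sometimes opened into food. That also stands: carrying the figure over is an assumption. Uncertainty about the peak time is, however, a reason for a wider window.

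A reader might infer from the 1–4 h range that most peaks fall outside the window and that Cmax,ss is lost. The documents do not support this. The range describes single doses; at steady state the modelled peak comes at about 1.9–2.1 h, and a 1 h sample already reads 93–97% of it. Nor does the exposure-response work in Exploratory Objective 2 lose much, since it uses Cmax,ss, Cmin,ss and AUCss.

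**Conclusion.** The point holds as a minor one. The preferred window and the protocol's own peak time are not reconciled, and the two sampling clusters are a weak basis for V/F, half-life and Tmax,ss. If sites keep to them, the relative SE of V/F and half-life is roughly twice what a 0.5–4 h window would give (33.7/15.6 = 2.2 to 37.9/20.0 = 1.9 for V/F; 28.3/15.0 = 1.9 to 34.2/19.6 = 1.7 for half-life). For Tmax,ss it is about 1.3 to 1.4 times (53.6/42.3 and 36.8/25.5). The parameters remain estimable; they are less precise. Cmax,ss, CL/F and AUCss are little affected.

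The sizes rest on the one-compartment model, the half-life and the variances, none of which is in the documents, and on sites following the preference. The direction for V/F and half-life was the same in every comparison that kept the trough sample. The MOP and the PK Analysis Plan, which may say more about sampling, were not available. Primary efficacy and safety are untouched.

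**What to change.** In Section 6.7.1, Table 1 footnote 2 and the MOP, widen the preferred post-dose window to 30–240 minutes, ask sites to spread children across it, and keep a pre-dose trough sample for every child. State the number of draws per visit, since the or in footnote 2 leaves it open.
- *If a trough is also drawn:* the post-dose draw can be split, 0.5–2 h at one visit and 2–4 h at the other.
- *If there is one draw per visit:* keep one visit for the trough and spread the single post-dose draw over 0.5–4 h across children. Do not split both visits into post-dose draws.

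If there is a reason for closing at 2 h, give it instead. Section 10.4.3 should also say whether Tmax,ss is expected to be estimable.

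The cost is wording in three places, with no extra draw. The downside is that some families will be drawn later after the dose.

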6.7.2 Clinical Laboratory Determinations

The following hematologic values are required to be collected at screening: hematocrit, white blood cell (WBC) count, platelet count, and differential. The following serum chemistry values are required to be collected at screening: blood urea nitrogen (BUN), serum creatinine, potassium, sodium, AST, ALT, total bilirubin, and albumin. Thyroid function will be measured, including TSH and free thyroxine, T4. If these values were obtained via standard of care within 30 days of enrollment, these values can be used; otherwise, they must be obtained prior to enrollment.

At the Week 4 visit, clinical labs will be collected to assess for liver toxicity: LFTs. If the blood sample for LFTs cannot be drawn at the Week 4 visit for any reason (e.g., parent/legal guardian request to cease blood draw attempts, participant uncompliance, etc.), the clinical lab draw for LFTs may be collected at the Week 8 visit.

6.8 Dose Escalation Assessments

Every 5 (+ 2) days through Week 7, just prior to each dose escalation assessment, parent/legal guardian will be asked to measure HR and BP using the device given to them from the study team at the time of randomization. A telephone or in-person assessment by the treating clinician will occur to determine dose escalation. If the participant reaches the maximum dose of 3 mg/day, prior to Week 7, no dose escalation will occur. Alternatively, a CGI-I will be determined by the treating clinician and any score of 3 or worse (higher) will warrant dose escalation, provided no significant safety concerns exist. AEs and safety ESIs will be recorded to assess safety.

Clinically significant findings that would prevent dose escalation include, but are not limited to:

- CGI-I score of 2 or 1
- HR and BP values that are considered unsafe to dose escalate:
 - Clinically significant hypotension, defined as systolic BP percentile less than the 5th percentile.^{31,34} This corresponds to systolic BP percentiles for neurotypical children under the 8th percentile for males and under the 10th percentile for females.
 - Clinically significant bradycardia, defined as HR > 2 SD below mean for age
- Any AEs or safety ESIs that make it unsafe to dose escalate, at the discretion of the treating clinician
- Any other finding that indicates it is not safe to dose escalate, at the discretion of the treating physician and/or principal investigator (PI).

6.9 Clinical Outcome Assessments

Identifying measures to evaluate cognition and behavior in children with IDD and DS specifically, within clinical trials has traditionally been challenging.¹⁰ Leading clinician and scientist experts were assembled by the NIH to review existing measures and identify those that are appropriate for clinical trials in individuals with IDD and specifically DS.¹¹ The ABC, ESS-CHAD, and CSHQ will be collected using Electronic Participant Reported Outcomes (ePRO), see Section 15.3. Details regarding which individual(s) complete(s) each measure at the various visits are included in [Table 2](#).

Table 2. Frequency of measures and who completes each measure.

Measure	Frequency Parent/ Legal Guardian Completes	Frequency Clinician Completes
ABC (Section 0)	Screening, Week 4, Week 8, Early Withdrawal	N/A
Sleep Assessments (Section 6.9.2)	Day 1, Week 4, Week 8	N/A
CGI-I (Section 6.9.3)	N/A	Weeks 1-8, Early Withdrawal
CGI-S (Section 6.9.3)	N/A	Screening

6.9.1 Aberrant Behavioral Checklist (ABC)

The ABC is a rating scale that measures the severity of a range of problem behaviors commonly observed in individuals with IDD.¹² It is an empirically developed scale designed to measure psychiatric symptoms and behavioral disturbance exhibited by individuals with IDD across 5 domains: Irritability (Agitation, & Crying); Lethargy/Social Withdrawal; Stereotypic Behavior; Hyperactivity (Noncompliance); and Inappropriate Speech, and it has been used extensively in pediatric and adult behavioral and psychiatric studies due to its high reliability and validity.^{11,13} The ABC-H subscale has been the primary outcome measure in the only trial of GIR for ADHD and disruptive behaviors in children with DS, as well as in several trials of ADHD with and without ASD in children.¹⁴⁻¹⁷ For this study, the ABC will be completed by parent(s)/legal guardian(s).

6.9.2 Sleep Assessments

Epworth Sleepiness Scale: The ESS-CHAD is a self-administered 8-item questionnaire to assess daytime sleepiness. For this study, the parent/legal guardian will complete the assessment.

Child's Sleep Habits Questionnaire (CSHQ): The abbreviated CSHQ includes 35 items that are divided into the following sections: bedtime, sleep behavior, waking during the night, and morning wake up. For this study, the parent/legal guardian will complete the assessment.

6.9.3 CGI-Severity for Eligibility and CGI-Improvement for Improvement

The CGI is a well-established research rating tool that can be used in the context of any psychiatric disorder. It consists of two parts including a 7-item assessment of the severity of psychopathology (CGI-S) and a 7-item assessment on the change from initiation of treatment (CGI-I). The CGI-S asks raters to indicate the frequency and severity of symptoms over a 7 day rating timeframe and establishes a baseline for each participant.¹⁸ The CGI-I is an objective measure of a single participant's change (improvement or worsening) compared to baseline. For this study, the CGI assessments will be completed by clinicians.

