10.4.1 Primary Analysis

The primary objective of this study is to determine GIR efficacy for the treatment of hyperactivity, inattention, and impulsivity in children with DS using the ABC-H scale. This objective will be evaluated using the endpoint of change from baseline to Week 8 of the ABC-H subscale score. The ABC-H subscale is a continuous scale with a minimum score of zero to a maximum score of 48, so the primary analysis will be conducted assuming a normal distribution. A mixed effect model analysis will be conducted to compare the change in ABC-H subscale score from baseline. Analysis will be conducted in SAS statistical analysis software using a PROC MIXED procedure. Fixed effects in the model will include indicator for the treatment assignment (GIR vs. placebo), baseline ABC-H score, and assessment week. To account for the correlation of longitudinal scores collected at baseline, Week 4, and Week 8, a participant level random intercept will be included in the model. The primary endpoint (effect size, p-value, and 95% confidence interval) of difference in the change from baseline to Week 8 of the ABC-H subscale will be evaluated using a contrast statement in the model. Additional analysis to evaluate impact of other covariates, including age, sex, weight, comorbid diagnosis of ASD, use of alternative agent(s) to treat ADHD, site, cumulative dose, demographics, may also be conducted. A sensitivity analysis may also be performed to determine how the missing data mechanism affects the primary outcome results.

Secondary efficacy outcome measures: GIR effectiveness for the treatment of hyperactivity, impulsivity, and inattention in children with DS will also be assessed using change from baseline to Week 4 of the ABC-H subscale score and with the CGI-I specific to hyperactivity, inattention, and impulsivity behaviors. The change from baseline to Week 4 of the ABC-H subscale score will be analyzed using the mixed effects model described above. The CGI-I is measured on a 7 point Likert scale from “very much improved” to “very much worse.” The proportion of participants with a CGI-I of “1-very much improved” or “2-much improved” will be analyzed as a dichotomous outcome. These dichotomized outcomes will be analyzed using a generalized linear mixed model with binary distribution and logit link. All mixed models for secondary efficacy endpoints will include covariates identified above for the analysis of primary efficacy endpoint.

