10.6 Sample Size Considerations

The primary hypothesis is that change from baseline on ABC-H subscale over the 8-week trial will be greater in GIR compared to placebo. In a randomized clinical trial of GER in ASD,¹⁵ the guanfacine group showed a 43.6% decline in scores on the ABC-H subscale (mean scores of 34.2 at baseline to 19.3 at week 8 visit) compared with a 13.2% decrease in the placebo group (mean scores of 34.2 at baseline to 29.7 at week 8 visit; effect size Cohen's $d=1.67$). Modal doses of GER in this trial were 3 mg/day (range 1 mg/day to 4 mg/day). In another single arm GIR trial,⁶ Capone et al. reported a mean decline in ABC-H scores from baseline to follow-up of 25% (mean scores of 29 at baseline to 21.2 at follow-up visit, Cohen's $d = 0.9$) over an average of 21 weeks. Average doses of GIR in the Capone study were 1.1 (± 0.5) mg/day, reflecting the more conservative approach to dose escalation in this patient population with DS. A decline in the ABC-H scale scores in the guanfacine group ranged from 25% to 43% across these studies. Although there are no identified studies characterizing a "clinically meaningful change" in ABC-H scores, the open-label Capone study revealed a significant improvement in target behaviors characterized as "inattention" and "activity" with the associated 25% improvement in ABC-H scores.⁶

Based on these studies, a conservative effect size of Cohen's $d = 0.9$ was assumed for the current randomized trial, which will be equivalent to assuming a 31.3% decline in the guanfacine arm (mean scores of 30 at Baseline to 20.6 at Week 8, $SD = 6$) compared with a 13.3% decrease in the placebo arm (mean scores of 30 at Baseline to 26 at Week 8, $SD = 6$). A sample size of 48 will achieve greater than 80% power to reject the null hypothesis of zero effect size when the population effect size is 0.90 and the significance level (alpha) is 0.050 using a two-sided two-sample equal-variance t-test. If a 20% dropout is assumed, N=60 participants will need to be enrolled.

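### The CGI-I responder model adjusts for parent-rated baseline ABC-H but omits the clinician-rated baseline CGI-S already collected at Screening: a minor precision point for a secondary endpoint

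*Combined protocol and SAP*

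**What the plan says.** CGI-I response (a score of 1 or 2, at Week 4 and at Week 8) is a secondary efficacy endpoint (Sections 3 and 10.2.1). Section 10.4.1 analyses it with a logistic mixed model and sets the covariates by reference: "All mixed models for secondary efficacy endpoints will include covariates identified above for the analysis of primary efficacy endpoint". The primary model's list is: "Fixed effects in the model will include indicator for the treatment assignment (GIR vs. placebo), baseline ABC-H score, and assessment week". A further list of covariates that may be explored covers age, sex, weight, ASD, other ADHD treatment, site, cumulative dose and demographics. CGI-S is named in neither list.

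Section 6.9.3 describes the CGI-S as rating the frequency and severity of symptoms "over a 7 day rating timeframe and establishes a baseline for each participant", and the CGI-I as the change relative to baseline. Both are clinician-rated (Table 2). Both are specific to hyperactivity, inattention and impulsivity (Section 5.2, inclusion criterion 5b; Section 3). The CGI-S is collected at Screening only. A score of at least 4 is required for entry, so every eligible randomized child should have a pre-treatment value between 4 and 7. Section 10.4 leaves the detail of the secondary analyses to an SAP due before data lock.

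**The concern.** CGI-I response is the only clinician-rated efficacy endpoint. The baseline severity term in its model comes from a different rater (the parent) and a different instrument (the ABC-H). The clinician's own severity rating is left out, although the trial already holds it. Randomization is stratified by site only (Section 5.4.1), so the design does not balance severity. If more severely affected children are less (or more) likely to be rated responders, omitting CGI-S leaves explainable variation in the outcome. It also leaves in the estimate whatever part of a chance CGI-S imbalance the ABC-H does not capture.

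The deferral to a later SAP does not settle this. Section 10.4.1 already fixes the covariate rule, and an SAP that follows it would repeat the omission.

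**Working it through.** **1. The plan's own figure (Section 10.6).** The plan states: "A sample size of 48 will achieve greater than 80% power", "when the population effect size is 0.90" and "the significance level (alpha) is 0.050 using a two-sided two-sample equal-variance t-test". The assumed means are "mean scores of 30 at Baseline to 20.6 at Week 8" (GIR) and "mean scores of 30 at Baseline to 26 at Week 8" (placebo), with SD 6.
- Effect size: (26 − 20.6)/6 = 5.4/6 = 0.90.
- 48 split 2:1 gives 32 and 16.
- Noncentrality: 0.90 × √(32 × 16/48) = 0.90 × 3.266 = 2.94, on 46 degrees of freedom. Power is 82.1% (83.6% by normal approximation).
- Enrolment: 48/(1 − 0.20) = 60.

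The stated figures reproduce. They concern ABC-H only; the plan gives no power figure for CGI-I.

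**2. Chance imbalance in severity.** The SE of a standardized baseline difference is √(1/32 + 1/16) = √0.09375 = 0.306 SD. Hence P(|difference| > 0.3 SD) is about 33%, and P(|difference| > 0.5 SD) about 10%. If CGI-S and ABC-H correlate at ρ, the part that ABC-H does not explain has SE of roughly 0.306 × √(1 − ρ²): 0.29 SD at ρ = 0.3 and 0.24 SD at ρ = 0.6.

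**3. CGI-I power without covariates, 32 versus 16.** All response rates here are assumptions. Placebo versus GIR: 20% vs 50% gives 52%; 15% vs 50% gives 68%; 20% vs 60% gives 78%; 10% vs 50% gives 83%.

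**4. Effect of adding CGI-S when ABC-H is already in the model.** Simulation of a single-visit logistic model with a likelihood-ratio test for treatment, 4,000 runs per setting, 32 versus 16. Assumptions not in the documents:
- response 20% on placebo and 60% on GIR;
- CGI-S of 4/5/6/7 in 50/35/13/2% of children;
- odds of response falling by a factor of 1 to 3 per SD of CGI-S;
- latent CGI-S/ABC-H correlation ρ of 0.3 or 0.6;
- ABC-H has no effect beyond CGI-S.

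| Odds factor per SD of CGI-S | ρ = 0.3: without → with CGI-S | ρ = 0.6: without → with CGI-S |
|---|---|---|
| 1 (no association) | 79.4 → 79.3% | 77.9 → 77.4% |
| 1.5 | 80.6 → 80.9% | 78.3 → 79.3% |
| 2 | 79.2 → 81.6% | 79.5 → 82.2% |
| 3 | 79.1 → 84.9% | 79.7 → 84.6% |

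The change runs from −0.5 to about +6 points.

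**5. Type I error.** With 30% response in both arms and ρ = 0.3, rejection was 5.2–5.5% without CGI-S and 5.6–5.8% with it.

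**6. Sparsity.** At 20% placebo response, the expected number of placebo responders is 16 × 0.20 = 3.2, and the chance of none is 0.80^16 = 2.8%. In the simulation, about 0.4–4% of runs were dropped for separation or non-convergence.

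Limits: one visit and no random intercept, whereas the plan specifies a mixed model.

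**The case against.** The strongest case against is that this is a covariate preference and not a flaw.

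- A reader might infer that CGI-I lacks adjustment for its own baseline. The documents do not support that. Section 6.9.3 describes two companion parts, one rating severity and one rating change. CGI-I has no baseline value, because each rating is already made against the child's starting state. The usual reason for adjusting an outcome for its own baseline therefore does not carry over directly. This stands.
- A reader might infer that power is lost. The documents give no association between CGI-S and CGI-I response, not even a direction. Entry restricts CGI-S to 4–7, and Screening may precede Day 1 by up to 29 days; both may weaken any association. This stands, and the gain must be stated as conditional.
- A reader might infer bias. Under randomization a chance imbalance is random error, already reflected in the interval and p-value. Step 5 shows no validity problem without CGI-S and no improvement with it. This stands.
- The model is sparse, and an added covariate has a price. This stands as a cost, but it is one parameter. Where CGI-S was unrelated to response, power fell by at most 0.5 points.
- The optional covariate list is open-ended and the SAP is still to come. Both make the change easy, but neither supplies it.

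**Conclusion.** The omission is real. However the reference to the primary model's covariates is read, CGI-S is not named. The consequence is limited to precision: a power change from about nil to +6 points, with the upper end reached only if the odds of response fall threefold per SD of CGI-S. Those figures rest on assumed response rates, severity mix and correlations. What the trial's size does establish, taking the planned 48 evaluable children at 2:1, is that a severity imbalance above 0.3 SD has about a one-in-three chance, and that the planned model removes only the part shared with ABC-H.

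The priority is minor: a secondary endpoint with no stated power target. The point stands because the matched clinician rating is already collected and including it costs almost nothing.

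**What to change.** In Section 10.4.1, and in the SAP that follows it, keep the existing sentence on secondary-model covariates and add: *The CGI-I models will additionally include baseline CGI-S (linear) as a fixed effect.* Add rather than replace, because the existing sentence is what carries treatment, baseline ABC-H and assessment week into these models. If the sponsor prefers to leave CGI-S out, the SAP should say why.

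No new data are needed. The costs are one extra parameter in a small, sparse binary model and a change in what is estimated: in a logit model the treatment odds ratio becomes conditional on CGI-S as well as ABC-H. The covariate should therefore be fixed before unmasked data are reviewed. The data-lock deadline in Section 10.4 is not early enough to ensure this, since Section 4.2.2 unmasks participants, site staff and study administrators at each child's Week 8 visit.
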